4.6.2.1.7. Diabetic Retinopathy or Maculopathy

The diabetic retinopathy or maculopathy will be searched by MedDRA PTs from all TEAEs. The list of PTs for the search is provided in [Appendix 7](#) (Section 6.7). A summary of treatment-emergent retinopathy or maculopathy by PT will be provided.

4.6.2.1.8. Peripheral Edema

The peripheral edema will be searched by MedDRA PTs (see Section 6.8) from all TEAEs. The number and percentage of participants experiencing treatment-emergent peripheral edema will be summarized by PT.

4.6.2.1.9. Hypokalemia

The TEAEs of hypokalemia will be identified by narrow terms in Hypokalaemia SMQ (20000233). A summary of the number of participants with TEAEs meeting the SMQ narrow search criteria will be provided by PT.

4.6.2.1.10. Hyperglycemia

The study treatments were designed as the treatment of hyperglycemia for diabetes patients. Therefore, the hyperglycemia is usually not reported as an AE in diabetes studies. However, if a participant develops severe, persistent hyperglycemia after randomization, a rescue therapy will be considered. A listing of participants who receive rescue medication will be provided.

4.6.2.1.11. Major Adverse Cardiovascular Events (MACE)

Potential cerebrocardiovascular events will be identified by the investigative site or by a medical review conducted by the sponsor or designee. A blinded external Clinical Event Committee will adjudicate the events in a consistent and unbiased manner. Events include:

- Death;
- Cardiac ischemic events including:
 - myocardial infarction, and
 - hospitalization for unstable angina;
- cerebrovascular events including:
 - stroke, and

- transient ischemic attack;
- hospitalization for heart failure; and
- coronary revascularization procedure.

Only confirmed MACE by the adjudication committee will be considered as AESIs. A listing of MACE events reported by investigator, including reported term and adjudication results, will be provided.

4.6.2.1.12. Medication Error of Interest

Medication Errors of Interest (MEI) are defined as medication error AEs (SMQ 20000224 - narrow and broad terms) that meet the criteria of important protocol deviations (IPD) indicative of multiple dose, according to the Trial Issue Management Plan (TIMP). These events are considered IPDs and special interest because of their potential to impact participant's safety.

MEI AEs are categorized as IPDs of "Investigational Medicinal Product and/or Investigational Device". Screening and identification of MEI AEs will occur during routine review of individual trial protocol deviations and trial level safety reviews.

The number and percentage of participants reported with MEI will be analyzed.

A listing of MEI will be provided. This listing will indicate if severe hypoglycemia or P-R hypoglycemia occurred after the MEI.

4.6.3. Additional Safety Assessments

4.6.3.1. Hypoglycemic Events

4.6.3.1.1. Participant-Reported Hypoglycemic Events

The following types of hypoglycemia events will be derived in the analysis data sets: documented hypoglycemia as Level 1, Level 2, and Level 3 (severe hypoglycemia) according to definitions based on the American Diabetes Association criteria where:

- Level 1: glucose <70 mg/dL (3.9 mmol/L) and ≥ 54 mg/dL (3.0 mmol/L);
- Level 2: glucose <54 mg/dL (3.0 mmol/L); and
- Level 3: severe hypoglycemia (confirmed by the investigator to be an event that required assistance for treatment).

Level 2 and Level 3 events are considered clinically significant hypoglycemia. Therefore, the analysis on a composite of Level 2 and Level 3 (denoted as Level 2/3) hypoglycemia will also be conducted.

Hypoglycemia will also be further classified into:

- nocturnal hypoglycemia (occurs between midnight and 0600); and
- non-nocturnal hypoglycemia (occurs between 0600 and midnight).

If a hypoglycemic event is within 60 minutes of another hypoglycemic event, it is considered as a continuation of the previous event. If there are multiple hypoglycemic events within 60 minutes of each other, then all events will be combined into a single event, which has the:

- earliest date time;
- minimum glucose value, if applicable;
- maximum severity (Level 1, 2 or 3);
- combined all symptoms and outcomes; and
- time of nocturnal if any of the events is nocturnal;

of the multiple hypoglycemic events.

The combined event starts from the first record with Level 1, 2 or 3, and ends when there are no more events for at least 60 minutes.

The evaluation of potential persistent-recurrent hypoglycemia events will be through assessment of the clinically significant events confirmed by investigators based on clinical judgment and through events identified by a pre-specified criteria (Section 4.6.2.1.2 and [Appendix 10](#), Section 6.10) using information based on the participant-reported hypoglycemia.

The details of planned analyses are provided in the below table.

Endpoint	Analysis Period	Statistical Method
Event rate of Level 1 hypoglycemia events (events/participant/year): • All documented	Baseline, 0-6, 0-12, 0-26, 0-52, 12-26, 26-52 weeks, post-treatment period	Negative binomial regression with treatment and baseline HbA1c as covariates, log (exposure/365.25 days) as the offset in the model.
Event rate of Level 2 hypoglycemia events (events/participant/year): • All documented	Baseline, 0-6, 0-12, 0-26, 0-52, 12-26, 26-52 weeks, post-treatment period	Negative binomial regression with treatment and baseline HbA1c as covariates, log (exposure/365.25 days) as the offset in the model. If the number of events is too small to run the negative binomial regression, exposure adjusted rate calculated by total number of events divided by total exposure for individual patients will be provided and the empirical method (see Appendix 9 [Section 6.9] for details) will be used for treatment comparison.
Event rate of Level 3 hypoglycemia events (events/participant/year): • All documented	baseline, 0-26, 0-52, 26-52 weeks, post-treatment period	Negative binomial regression with treatment and baseline HbA1c as covariates, log (exposure/365.25 days) as the offset in the model. If the number of events is too small to run the negative binomial

Endpoint	Analysis Period	Statistical Method
		regression, exposure adjusted rate calculated by total number of events divided by total exposure for individual participants will be provided and the empirical method (see Appendix 9 [Section 6.9] for details) will be used for treatment comparison.
Event rate of Level 2/3 hypoglycemia events (events/participant/year): 
 • All documented • Nocturnal • Non-nocturnal 	baseline, 0-6, 0-12, 0-26, 0-52, 12-26, 26-52 weeks, post-treatment period	Negative binomial regression with treatment and baseline HbA1c as covariates, log (exposure/365.25 days) as the offset in the model. If the number of events is too small to run the negative binomial regression, exposure adjusted rate calculated by total number of events divided by total exposure for individual patients) will be provided and the empirical method (see Appendix 9 [Section 6.9] for details) will be used for treatment comparison. The plots of the mean cumulative functions (MCFs) by each treatment arm will also be created. The population mean for cumulative number of events up to time t, $M(t)$, will be estimated using a nonparametric estimation method described by Nelson (2003).
Incidence of Level 1 hypoglycemia events: 
 • All documented 	Baseline, 0-6, 0-12, 0-26, 0-52, 12-26, 26-52 weeks, post-treatment period	Logistic regression with treatment and baseline HbA1c as covariates.
Incidence of Level 2 hypoglycemia events: 
 • All documented 	Baseline, 0-6, 0-12, 0-26, 0-52, 12-26, 26-52 weeks, post-treatment period	Logistic regression with treatment and baseline HbA1c as covariates.
Incidence of Level 3 hypoglycemia events: 
 • All documented 	Baseline, 0-26, 0-52, 26-52 weeks, post-treatment period	Logistic regression with treatment and baseline HbA1c as covariates.
Incidence of Level 2/3 hypoglycemia events: 
 • All documented 	Baseline, 0-6, 0-12, 0-26, 0-52, 12-26, 26-52 weeks, post-treatment period	Logistic regression with treatment and baseline HbA1c as covariates.

Endpoint	Analysis Period	Statistical Method

 • Nocturnal • Non-nocturnal 		
Potential persistent-recurrent hypoglycemia events 
 • identified by investigator • identified by pre-specified criteria (defined in Appendix 10 [Section 6.10]) 	Safety analysis period (see definition in Section 4.6)	The number of participants with at least one event will be summarized and compared by Fisher's exact test. The number of events will also be provided. Listings of the events will also be provided.

Abbreviations: HbA1c = hemoglobin A1c; Level 2/3 = Level 2 and Level 3 composite.

Note: The hypoglycemia yearly rate during defined period is calculated by the number of hypoglycemia within the period/number of days patient at risk within the period * 365.25. For rare events, 100-year rate will be provided. The hypoglycemia incidence during defined period indicates if the patient has at least 1 hypoglycemia events within the period (Yes/No).

Note: For treatment group comparison at baseline, baseline HbA1c is not included in the model.

A sensitivity analysis will be done for selected hypoglycemic endpoints where all hypoglycemic events are considered one hypoglycemic event until a succeeding glucose value is ≥ 70 mg/dL.

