6.3. Measures to Minimize Bias: Randomization and Blinding

Randomization and stratification

All participants will be centrally assigned to randomized study intervention using an IWRS. Before the study is initiated, the login information and directions for the IWRS will be provided to each site.

Participants will be randomly assigned in an 1:1 ratio to LY3209590: insulin degludec.

Participants will be stratified based on

- country
- HbA1c stratum at Visit 1 (<8% and \geq 8%)
- sulfonylurea use at randomization (Yes/No), and
- GLP-1 RA use at randomization, regardless of oral or injectable administration (Yes/No).

Blinding

This is an open-label study. Investigators and participants will be unblinded to the assigned treatment groups.

The Lilly study team members who are closely involved in data interpretation and analysis planning will remain blinded throughout the course of the study. Only a minimum number of Lilly personnel will see the randomization table and treatment assignments before the study is complete.

The investigator should make every effort to preserve the blinding when contacting the Lilly study team members, including the Lilly clinical research physician or scientist.

Unblinded reviews

External committees reviewing unblinded data during the study are described in Section 10.1.5.

An early PK/PD unblinded transfer may also be conducted. Only a small group of personnel can be unblinded to the data for the potential PK/PD analysis and must keep information confidential until the planned unblinding of the trial.

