1.2. Study Design

- This is a Phase 3, parallel-design, open-label, randomized control study to evaluate the efficacy and safety of LY3209590 administered once-weekly compared to insulin degludec administered daily.
- The study includes a 3-week screening and lead-in period, a 52-week treatment period, and a safety follow-up period approximately 5 weeks after the last visit in the treatment period.
- Assignment to treatment groups will be determined by an interactive web-response system (IWRS). Participants will be randomly assigned to 1 of the 2 treatment groups in 1:1 ratio (LY3209590: insulin degludec) at Visit 3 (Week 0). The number of participants in each subpopulation of participants using or not using GLP-1 RA will be approximately 50% of the study population with balanced treatment assignment. Stratification will be by country, HbA1c stratum at Visit 1 (Week -3) (<8.0%, ≥8.0%), sulfonylurea use at randomization, and GLP-1 RA use at randomization, regardless of oral or injectable administration.
- Rescue therapy will be considered during the treatment period if the participants meet the protocol criteria of severe, persistent hyperglycemia.
- If study intervention is permanently discontinued, the participant will be encouraged to continue participation in the study for continued monitoring. Both efficacy (including HbA1c) and safety data will continue to be collected per the schedule of activities in the protocol.
- Participants will collect blinded CGM for 2 weeks prior to Visit 3 (Week 0), for 4 weeks prior to Visit 7 (Week 4), Visit 15 (Week 12), Visit 24 (Week 26), Visit 31 (Week 52), and for 4 weeks after Visit 31 (Week 52). Dexcom G6 system provides readings every 5 minutes. In China, instead of the Dexcom G6 system, the Libre Freestyle H system which provides readings every 15 minutes will be used. Main analyses for CGM measurements will be conducted based on data from the Dexcom G6 system.

2. Statistical Hypotheses

Primary Hypothesis

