Analysis Model	
After the imputation, the observed and imputed data will be analyzed by the ANCOVA model using treatment, strata (country, GLP-1 RA treatment at randomization, and SU use at randomization), and baseline value of the dependent variable as independent variables. The statistical inference will be based on the multiple imputation framework by Rubin (1987).
	
The MMRM model will include treatment, strata (country, GLP-1 RA treatment at randomization, and SU use at randomization), visit and treatment-by-visit interaction as fixed effects, and baseline of the dependent variable as a covariate. The Kenward-Roger approximation will be used to estimate denominator degrees of freedom for the MMRM models. An unstructured covariance structure will be used to model the within-participant errors. If this structure fails to converge, the following covariance structures will be used in order until one converges:
 
 1. Toeplitz with heterogeneity 2. autoregressive with heterogeneity 3. compound symmetry with heterogeneous variances 4. Toeplitz 5. Autoregressive 6. compound symmetry without heterogeneous variances.

Abbreviation: ANCOVA = analysis of covariance; MMRM = mixed model repeated measurement.

The 2-sided 95% CI of the LS mean difference (LY3209590 – insulin degludec) in the HbA1c change from baseline to Week 52 (Visit 31) will be estimated. For both estimands, LY3209590 will be declared noninferior to insulin degludec if the upper limit of the 2-side 95% CI for the LS mean difference in the HbA1c (measured in %) change from baseline is below NIM of +0.4%. In addition, the 95% CI for the LS mean difference will be compared to an alternative NIM of +0.3%.

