Incidence of Level 1 or Level 2 hypoglycemic events: 
 • 24-hour 	Baseline, 0-4, 8-12, 22-26, 48-52, 0-52 weeks (combine all sessions during treatment period), post-treatment period	Logistic regression with treatment and baseline HbA1c as covariates. The total number of episodes, number of episodes that includes Level 2 hypoglycemia episodes, and number of episodes that include glucose readings <54 mg/dL (3.0 mmol/L) but no Level 2 hypoglycemia episodes will be summarized for each CGM session.
Incidence of Level 2 hypoglycemic events: 
 • 24-hour 	Baseline, 0-4, 8-12, 22-26, 48-52, 0-52 weeks (combine all sessions during treatment period), post-treatment period	Logistic regression with treatment and baseline HbA1c as covariates.

Endpoint	CGM Session	Statistical Method
Incidence of Level 2 hypoglycemic events ending with ≥ 70 mg/dL: • 24-hour	Baseline, 0-4, 8-12, 22-26, 48-52, 0-52 weeks (combine all sessions during treatment period), post-treatment period	Logistic regression with treatment and baseline HbA1c as covariates.
Duration of Level 1 or Level 2 hypoglycemic events: • 24-hour	Baseline, 0-4, 8-12, 22-26, 48-52, 0-52 weeks (combine all sessions during treatment period), post-treatment period	The MMRM model will include treatment, strata (country, baseline HbA1c stratum ($<8.0\%$, $\geq 8.0\%$)), GLP-1 RA treatment at randomization, and SU use at randomization), time and treatment-by-time interaction as fixed effects, and baseline duration as a covariate. For 0-52 weeks: ANCOVA model will include treatment, strata and baseline duration. For Baseline and post-treatment period: ANOVA models only include treatment.
Duration of Level 2 hypoglycemic events: • 24-hour	Baseline, 0-4, 8-12, 22-26, 48-52, 0-52 weeks, post-treatment period	Same models as for Level 1 or Level 2 hypoglycemic events. A listing will be provided for participants with Level 2 hypoglycemia episodes lasting >360 minutes
Duration of Level 2 hypoglycemic events ending with $BG \geq 70$ mg/dL: • 24-hour	Baseline, 0-4, 8-12, 22-26, 48-52, 0-52 weeks, post-treatment period	Same models as for Level 1 or Level 2 hypoglycemic events.

Abbreviations: HbA1c = hemoglobin A1c.

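### The hypoglycemia rate models omit SU and GLP-1 RA use, both randomization strata, at a modest cost in precision

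*SAP*

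**What the plan says.** **Rate models.** For participant-reported Level 1, 2, 3 and 2/3 events, SAP 4.6.3.1.1 specifies "Negative binomial regression with treatment and baseline HbA1c as covariates", with the log of exposure in years as the offset. If events are too few, the Level 2, Level 3 and Level 2/3 rows fall back to the empirical method of Appendix 9. The Level 1 row has no fallback. The CGM event-rate models in SAP 4.6.3.1.2 use the same covariates.

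**Incidence models.** SAP 4.6.3.1.1 specifies "Logistic regression with treatment and baseline HbA1c as covariates".

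**Randomization.** Protocol 6.3 stratifies by country, screening HbA1c stratum, "sulfonylurea use at randomization (Yes/No), and" "GLP-1 RA use at randomization, regardless of oral or injectable administration (Yes/No". SAP 1.2 restates this.

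**Other models in the SAP.** The primary HbA1c models (SAP 4.3.2) include "strata (country, GLP-1 RA treatment at randomization, and SU use at randomization". The model for duration of CGM hypoglycemia (SAP 4.6.3.1.2) includes country, HbA1c stratum, "GLP-1 RA treatment at randomization, and SU use at randomization), time and treatment-by-time interaction as fixed effects".

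**Subgroup models.** SU use enters the Level 2/3 rate model as a subgroup with its interaction (SAP 4.7.2.3). For GLP-1 RA use, SAP 4.7.2.1 takes the variables of 4.6.3.1 and adds only the interaction with treatment.

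**The concern.** Background SU and GLP-1 RA use could plausibly predict hypoglycemia, and the plan treats both as relevant: each is a stratification factor and each defines a hypoglycemia subgroup analysis. If a prognostic factor is left out of a negative binomial model, the variation it explains goes into the dispersion parameter and the interval for the rate ratio widens. Both covariates are already collected, so precision would be lost without any saving in data.

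Consistency is also affected. CGM hypoglycemia duration is adjusted for the strata, while event rates, from the diary or from CGM, are not. In addition, the GLP-1 RA interaction model in SAP 4.7.2.1 is built on a base model that has no GLP-1 RA term.

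**Working it through.** **Plan's own figure.** There is none. Neither document gives a power statement, event rate or dispersion for hypoglycemia.

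**Inputs from the documents.** 888 participants randomized 1:1, so 444 per arm; about 50% using GLP-1 RA (Protocol 9.5).

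**Assumed inputs.** Annual control rate μ of 0.4 or 0.6; dispersion k of 3 or 4; SU share of 25% or 40%; SU rate ratio of 1, 2 or 3; GLP-1 RA rate ratio of 1, 0.7 or 0.6; treatment rate ratio of 0.65; one year of exposure each. Baseline HbA1c is left out of both models compared.

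**Step 1: the mechanism in one scenario** (μ = 0.4, k = 4, SU share 25%, SU ratio 2, GLP-1 RA ratio 0.7).

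- With the factors in the model, the variance of the log rate ratio is 1 / [444 × Σ w/S]. Here w is the stratum share and S = (1/μ_control + k) + (1/μ_treated + k) in that stratum.
- The mean relative rate is (0.75 + 0.25×2) × (0.5 + 0.5×0.7) = 1.0625. The four stratum control rates are therefore 0.4 × (1, 0.7, 2, 1.4)/1.0625 = 0.376, 0.264, 0.753, 0.527.
- S = 14.74, 17.63, 11.37, 12.82, with w = 0.375, 0.375, 0.125, 0.125. Then Σ w/S = 0.0674, and the SE is √[1/(444 × 0.0674)] = 0.183.
- Without the factors, dispersion rises to about (1 + k)h − 1, where h is the mean squared relative rate divided by the squared mean. Here h = (1.75/1.5625) × (0.745/0.7225) = 1.155 and dispersion is 5 × 1.155 − 1 = 4.77. The SE is √[(2.5 + 4.77 + 3.846 + 4.77)/444] = 0.189.

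The fitted models in step 2 reproduce the adjusted value (0.1828) but give 0.1851 unadjusted. The moment formula therefore overstates the loss, and the fitted results are the ones to use.

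**Step 2: fitted negative binomial models** (maximum likelihood, 800 simulated trials per scenario, arms balanced on both factors).

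| μ | k | SU share | SU ratio | GLP-1 RA ratio | SE without | SE with | Without/with |
|---|---|---|---|---|---|---|---|
| 0.4 | 4 | 25% | 2 | 0.7 | 0.1851 | 0.1828 | 1.012 |
| 0.4 | 4 | 40% | 2 | 0.7 | 0.1858 | 0.1835 | 1.012 |
| 0.4 | 4 | 25% | 3 | 0.6 | 0.1935 | 0.1877 | 1.031 |
| 0.6 | 3 | 40% | 3 | 0.6 | 0.1650 | 0.1587 | 1.040 |
| 0.4 | 4 | 25% | 1 | 1 | 0.1803 | 0.1804 | 1.00 |

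In the four prognostic scenarios power rose by about 1 to 4 points (0.641 to 0.678 in the first row), with Monte Carlo error of about 1.7 points per estimate.

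**Step 3: lower dispersion, SU only** (40% on SU, rate 0.3 or 0.6 without SU, k from 1 to 3, treatment rate ratio 0.8, 12% stopping early, 150 trials per scenario). Omitting SU raised the SE by 1.3% to 2.5% if SU doubles the rate and by 3.4% to 6.6% if SU triples it. The 6.6% occurs at k = 1 and rate 0.6.

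**Step 4: logistic incidence models in the step 2 scenarios.** With prognostic factors, adjustment raised the SE of the log odds ratio by 0.7% to 2.1% (for example 0.1585 to 0.1619). Power rose by about 1 point or less.

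**Step 5: the GLP-1 RA interaction model.** SAP 4.7.2.3 lists the subgroup factor and its interaction. In SAP 4.7.2.1 the body-weight model adds GLP-1 RA explicitly, and the dose and CGM models already contain it through their base model. Only the hypoglycemia model lists the interaction without the main effect. Fitted literally, that interaction term would take up any overall GLP-1 RA effect on the rate.

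**The case against.** Much of the opposing case stands. The unadjusted analysis is valid, and the loss is small and depends on inputs that the documents do not give. Level 2/3 hypoglycemia is listed under other secondary endpoints, has no multiplicity control (SAP 2.1) and no power statement, so no declared conclusion turns on a few percent of a standard error. The general safety MMRM in SAP 4.6 also omits the strata, and the SAP expects sparse events and convergence trouble in some periods. The SU and GLP-1 RA subgroup analyses will show differences by background therapy, but they do not replace the overall treatment estimate.

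A reader might infer four stronger things, none of which is supported:

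- **That the incidence intervals are also too wide.** Adjustment makes the standard error of the log odds ratio larger. The shift from a conditional odds ratio of 0.70 to about 0.704 to 0.716 (SU odds ratio 2 or 3) is the difference between a conditional and a marginal odds ratio. It is neither bias nor lost precision.
- **That the omission costs over 100 participants' worth of information.** This needs the 6.6% corner: 888 × (1 − 1/1.066²) ≈ 107. For ratios of 1.012 to 1.040 the same arithmetic gives about 21 to 67. The moment formula, pushed to dispersion 6, suggests SE reductions of up to about 12.5%, but step 1 shows that it overstates the loss.
- **That the main safety conclusion or type I error is at risk.** Nothing in the documents points to either.
- **That the planned GLP-1 RA interaction test is certainly wrong.** The listed terms lack the main effect, but the text does not show how the model will be programmed.

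**Conclusion.** The point holds for the rate models as a matter of efficiency and consistency. Two collected stratification factors are left out of the hypoglycemia rate models without explanation, while the HbA1c and CGM-duration models include them. The standard error of the log rate ratio is about 1% to 4% larger in most scenarios tried and up to about 7% at low dispersion with SU tripling the rate. There is no loss if the factors are not prognostic. All of these figures rest on assumed rates, dispersion, SU share and effects. No claim of lost precision holds for the logistic models.

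**What to change.** 1. In SAP 4.6.3.1.1, add SU use and GLP-1 RA use at randomization to the negative binomial models for Level 1, Level 2 and Level 2/3 rates, and keep baseline HbA1c. Continuous baseline HbA1c covers the HbA1c stratum in substance. Country can stay out because of sparse cells.
2. Make the same change to the CGM event-rate models in SAP 4.6.3.1.2, so that diary and CGM results are adjusted alike.
3. State the order of fallback: if the adjusted model does not converge, use the present HbA1c-only model, then the Appendix 9 method in the rows where the SAP provides it. Level 1 rates, and Level 1 or Level 2 rates from CGM, have no Appendix 9 fallback, so the HbA1c-only model is their last step.
4. With GLP-1 RA in the base model, the interaction model in SAP 4.7.2.1 has its main effect. Say so there.
5. Leave adjustment of the logistic incidence models optional. If it is adopted, state that the odds ratio is conditional on the added factors.

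The cost is SAP wording and two covariates already collected, with a slightly higher chance of non-convergence in sparse periods.
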